## PROTOCOL SUMMARY

Study Title	Urodynamic Feasibility Study (UDS)
Device Name and Indications for Use	
NeoTract® UroLift® System UL400. This device was cleared for marketing in the USA on September 13, 2013.
 
The UroLift System is indicated for the treatment of symptoms due to urinary outflow obstruction secondary to benign prostatic hyperplasia (BPH), including lateral and median lobe hyperplasia in men 45 years of age or older.

Study Goals	
 
• To prospectively collect urodynamic data prior to, and 3 months after PUL, with the UroLift System, and to assess the impact of the PUL procedure on prostatic obstruction, bladder health and other urodynamic parameters.
 
• To obtain evidence which may support the design of an expanded study.
 

Subject Population	
10 to 20 males over the age of 45, diagnosed with symptomatic benign prostatic hyperplasia (BPH) and intended for PUL procedure with the UroLift System will be enrolled at a single center.
 
Since this is the first study to assess the impact of PUL procedure using pressure flow studies, the population is planned to be similar to the population studied in the LIFT Study.

Study Design	
This is a prospective, non-randomized, single-arm, single-center study. This is the first exploratory study of the impact of PUL as measured by pressure flow urodynamic testing (UDS). UDS will be performed at screening and at the 3-month follow-up visits. UDS will include an assessment of obstruction and bladder health as measured by Qmax (maximum urinary flow rate) and Pdet (detrusor pressure) at Qmax, and Pdetmax (maximum voiding pressure), as well as capturing all other standard urodynamic parameters. UroCuff as an alternative form of urodynamics testing will be an optional test performance at baseline and at 3M follow-up.
 
In addition, standard BPH measures such as symptoms, quality of life, uroflowmetry and post void residual will be evaluated at the follow-up visits. The analysis of the 3-month data is intended to evaluate the possibility of expanding the scope of the study. There will be no formal hypothesis testing.

Study Title	Urodynamic Feasibility Study (UDS)
Inclusion Criteria	
 
• Male gender
 
• Diagnosis of symptomatic BPH
 
• Age <math>\geq</math> 45 years
 
• International Prostate Symptom Score (IPSS) <math>\geq</math> 13
 
• Peak urine flow rate <math>\leq</math> 12 ml/sec, voided volume <math>\geq</math> 125 ml
 
• Prostate volume <math>\leq</math> 80 cc per ultrasound
 

Key Exclusion Criteria	
Key exclusion criteria are listed below.
 
See Section 6.3 for the full, detailed list of selection criteria.
 
Subjects will be excluded for any of the following:
 
 
• In current urinary retention
 
• Post void residual (PVR) urine <math>></math> 250 ml
 
• Have obstructive or protruding median lobe of the prostate
 
• Active urinary tract infection at time of treatment
 
• Current gross hematuria
 
• Previous BPH surgical procedure
 
• Previous pelvic surgery or irradiation
 
• History of neurogenic or atonic bladder
 
• Stress urinary incontinence
 
• Biopsy of the prostate within the past 6 weeks
 
• History of prostate or bladder cancer
 
• Elevated PSA without ruling out prostate cancer
 
• History of compromised renal function or upper tract disease
 
• Known coagulopathies or subject on anticoagulants or antiplatelets other than aspirin <math>\leq</math> 100 mg (unless antiplatelets are withheld minimum 3 days prior to procedure)
 
• Use of medications known to affect urological function unless washed-out (see protocol list)
 
• Cystolithiasis within the prior 3 months
 
• History of co-morbidities that would affect having an elective urological procedure including: prostatitis, conditions that preclude the insertion of the UroLift System
 
• A known allergy to nickel, titanium, or stainless steel
 
• Unable or unwilling to complete all required questionnaires and follow up assessments
 
• Unable or unwilling to sign informed consent form
 
• Currently enrolled in any other investigational clinical research trial that has not completed the primary endpoint.
 

Anticipated Study Duration	
Protocol Completion	August 2018
IRB Submission	August 2018
IRB Approval	September 2018
First Patient In (FPI)	September 2018
Last Patient In (LPI)	February 2019 (20 subjects)
3-month Analysis	May 2019
Study Close	June 2019

## 1 STUDY DESIGN

### 1.1 Study Objectives

The aim of this feasibility study is to determine the impact of PUL using the UroLift System on standard pressure flow measures for men with BPH. Feasibility and safety objectives include:

- Feasibility – Assess changes in obstruction and bladder health after PUL with the UroLift System.
- Safety- Determined by the absence of any investigator-reported serious adverse events (SAEs) associated with the device or procedure

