#### 3.1 Sample Size Justification

As this is a feasibility study, a formal sample size calculation is not required. However, we estimate that the number of participants required to get an initial assessment of urodynamic parameters pre and post PUL with UroLift will be between 10 and 20.

---

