### **3.3 Statistical Methods**

No statistical hypothesis will be tested. Descriptive reports will be provided for this preliminary evaluation. Data will be expressed as the mean  $\pm$  SD for continuous variables and as frequencies for categorical variables.

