### **4.1 Adverse Events**

Adverse events will be summarized by overall adverse events (AEs), severe AEs (grade 3 or higher on CTCAE scale), AEs related to device and/or procedure, serious adverse events (SAEs), and SAEs related to device and/or procedure separately, and UADEs.

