### **4.2 Interim Analysis**

The Urodynamics Feasibility Study will enroll at least 10 patients and then an interim analysis of the urodynamic parameters may be conducted.

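### The safety objective is a zero-event criterion in 10 to 20 men: meeting it would still leave a related-SAE rate of up to 16.8% (20 men) or 30.8% (10 men) not excluded

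*Combined protocol and SAP*

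**What the plan says.** Section 1.1 gives two objectives. Feasibility is to assess change in obstruction and bladder health. Safety is "Determined by the absence of any investigator-reported serious adverse events (SAEs) associated with the device or procedure". Section 3.2, within the statistical part, repeats the safety bullet.

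Section 3.1 makes no formal sample size calculation and puts the number of men needed for an initial assessment of urodynamics "pre and post PUL with UroLift will be between 10 and 20". The Protocol Summary gives the same range, and its timeline assumes 20. Under Section 4.2 the study "will enroll at least 10 patients and then an interim analysis of the urodynamic parameters may be conducted".

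The analysis is descriptive. The Protocol Summary says "There will be no formal hypothesis testing", and Section 3.3 reports continuous data as mean and SD "and as frequencies for categorical variables". Section 4.1 summarises adverse events by class, including "AEs related to device and/or procedure, serious adverse events (SAEs), and SAEs related to device and/or procedure separately, and UADEs". The text supplied gives no acceptable SAE rate and plans no confidence interval for the safety objective.

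**The concern.** The feasibility bullet says what will be assessed. The safety bullet says what will settle the matter. It is the only objective with a verdict built in, and the verdict rests on a count of zero in a very small group.

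Three problems follow:

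- A zero count would satisfy the objective as written although a substantial true rate remains compatible with the data.
- The criterion is easier to satisfy with fewer men, and the plan leaves the number open between 10 and 20.
- It can also mislead against the device, because a single event in 20 men fails it even when the true rate is low.

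What is at stake is the conclusion about safety that the final report may draw. One of the study goals is "To obtain evidence which may support the design of an expanded study", so a statement that the safety objective was met could be carried forward with more weight than the data can bear.

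**Working it through.** The plan states no SAE rate, precision or power, so it has no figure of its own to reproduce. The check asks what each possible result would show.

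**Inputs**

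- Criterion: zero related SAEs (Sections 1.1 and 3.2).
- Number of men, n: 10 to 20 (Protocol Summary and Section 3.1). n = 15 is added as a midpoint.
- Confidence level: 95%, my assumption, since the plan sets none.
- True related-SAE rates, p: 2%, 5% and 10%, chosen only for illustration. The documents give none.
- All n men are treated and evaluable for safety. Fewer would widen every interval.

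**1. No events seen.** The exact (Clopper-Pearson) upper limit is 1 − 0.025^(1/n) two-sided, or 1 − 0.05^(1/n) one-sided.

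| n | Two-sided 95% upper limit | One-sided 95% upper limit |
|---|---|---|
| 20 | 1 − 0.025^(1/20) = 0.1684, or 16.8% | 1 − 0.05^(1/20) = 0.1391, or 13.9% |
| 15 | 1 − 0.025^(1/15) = 0.2180, or 21.8% | 1 − 0.05^(1/15) = 0.1810, or 18.1% |
| 10 | 1 − 0.025^(1/10) = 0.3085, or 30.8% (0.30850 before rounding is 0.308497) | 1 − 0.05^(1/10) = 0.2589, or 25.9% |

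As a cross-check, the binomial probability of zero events at each two-sided limit is 0.025, as it should be.

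**2. One event seen.** The Clopper-Pearson limits are the 2.5% quantile of Beta(1, n) and the 97.5% quantile of Beta(2, n − 1).

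- n = 20: 0.0013 to 0.2487, that is 0.1% to 24.9%.
- n = 10: 0.0025 to 0.4450, that is 0.3% to 44.5%.

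**3. Chance that the criterion is met.** This is the probability of no events, (1 − p)^n.

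| Assumed true rate p | n = 20 | n = 10 |
|---|---|---|
| 2% | 0.98^20 = 0.668 (67%) | 0.98^10 = 0.817 (82%) |
| 5% | 0.95^20 = 0.358 (36%) | 0.95^10 = 0.599 (60%) |
| 10% | 0.90^20 = 0.122 (12%) | 0.90^10 = 0.349 (35%) |

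At every rate the smaller study is more likely to meet the criterion. At p = 2% the criterion fails with probability 1 − 0.668 = 0.332 (33%) in 20 men and 1 − 0.817 = 0.183 (18%) in 10.

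**The case against.** The strongest reply is that the plan never uses the words met, failed or shown. The bullet could be read as naming the event of interest, with the real safety analysis in Section 4.1, which is descriptive and already gives the count of related SAEs. Nothing hangs on the bullet: there is no acceptable rate, no stopping or expansion rule, no mention of safety in the study goals, and the optional interim analysis covers only urodynamic parameters. The probabilities of meeting the criterion rest on assumed rates and describe a test the plan does not run. With zero events only an upper bound is informative, so the one-sided limits are a fair alternative. An interval for one safety count, in a plan that gives none for its main urodynamic measures, may look like a preference. The Protocol Summary also points to a Section 6.3 that is not in the text supplied, so fuller safety wording may exist elsewhere.

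Much of this stands, and it limits the weight of the point. The plan is descriptive, no decision is tied to the bullet, and the assumed rates only illustrate. The one-sided limits are lower, but 13.9% and 25.9% carry the same message.

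The reading of the bullet as a mere label does not stand. It makes safety depend on the absence of events, and Section 3.2 repeats this within the statistical part. Section 4.1 neither withdraws that rule nor states any precision. A descriptive study should report a count with its uncertainty, which is a reason to change the bullet. The interval is asked for here, and not for the other measures, because only this objective is written as a verdict.

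**Conclusion.** The concern holds. As worded, the safety objective turns a count into a yes or no that 10 to 20 men cannot support. After zero events, a true rate of about one in six (20 men) or three in ten (10 men) is still not excluded. After one event in 20 men, a failed objective would rest on an interval that reaches down to 0.1%.

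The limits depend on the 95% two-sided convention and on every enrolled man being treated and evaluable. They do not depend on the illustrative true rates.

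This should be fixed, but it is of modest severity. The Protocol Summary describes the device as already cleared for marketing, and related SAEs will be tabulated in any case. The point alleges neither a safety problem nor a calculation error. It concerns only what may be concluded about safety.

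**What to change.** In Sections 1.1 and 3.2, replace the safety bullet with:

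*Safety: number and proportion of treated men with a device- or procedure-related SAE, with an exact (Clopper-Pearson) two-sided 95% confidence interval.*

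In Section 4.1, add that interval to the related-SAE summary, with one sentence:

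*If no related SAE occurs, the result will be reported as 0 of n with the upper confidence limit, and not as safety shown.*

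The cost is two reworded bullets, one interval and one sentence. The one drawback for the sponsor is that, with zero events, the safety statement reads less favourably than it would under the current wording.

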### 1.2 Study Design

This is a prospective, non-randomized, single- arm, study. This is the first exploratory study of the impact of PUL as measured by pressure flow, urodynamic testing (UDS). UDS will be performed at screening and the 3-month follow-up visits and will include an assessment of obstruction and bladder health as measured by Qmax and Pdet@Qmax, and by Pdetmax, and other standard urodynamic parameters. Investigators have the option to use UroCuff, an alternative urodynamic test.

In addition, standard BPH measures such as symptoms, quality of life, uroflowmetry, and post void residual will be evaluated at screening and at the follow-up visits. The analysis of the 3-month data is intended to evaluate the possibility of expanding the scope of the study.

## 2 ENROLLMENT CRITERIA

### 2.1 Inclusion Criteria

Subjects enrolled in this clinical study must meet all the following criteria:

1. Male gender
2. Diagnosis of symptomatic BPH

- 
3. Age  $\geq$  45 years
  4. International Prostate Symptom Score (IPSS)  $\geq$  13
  5. Peak urine flow rate  $\leq$  12 ml/sec on a voided volume  $\geq$  125 ml
  6. Prostate volume to  $\leq$  80 cc per ultrasound

## 2.2 Inclusion Criteria

Subjects will be excluded from the study if any of the following conditions apply:

1. Current urinary retention
2. Post void residual (PVR) urine  $>$  250 ml
3. Have an obstructive or protruding median lobe of the prostate
4. Active urinary tract infection at time of treatment
5. Current gross hematuria
6. Previous BPH surgical procedure
7. Previous pelvic surgery or irradiation
8. History of neurogenic or atonic bladder
9. Stress urinary incontinence
10. Biopsy of the prostate within the past 6 weeks
11. Life expectancy estimated to be less than 1 year
12. History of prostate or bladder cancer
13. Elevated PSA without ruling out prostate cancer
14. History of compromised renal function or upper tract disease
15. Known coagulopathies or subject on anticoagulants or antiplatelets other than aspirin  $\leq$  100 mg (unless antiplatelets are withheld minimum 3 days prior to procedure)
16. Use of the following medications pre-screening (uroflow, questionnaires):
  - o Within 4 months of baseline assessment: estrogen, any drug producing androgen suppression, or anabolic steroids
  - o Within 3 months of baseline assessment: 5-alpha-reductase inhibitors
  - o Within 2 weeks of baseline assessment: alpha-blockers, gonadotropin-releasing hormonal analogs, anticholinergics or cholinergic medication or phenylephrine, pseudoephedrine, or imipramine medications
  - o Within 1 week of baseline assessment, unless documented on stable dose for  $\geq$  6 months: beta blockers, antidepressants, anticonvulsants, and antispasmodics
17. Cystolithiasis within the prior 3 months
18. History of co-morbidities that would affect having an elective urological procedure including: prostatitis, conditions that preclude the insertion of the UroLift System.
19. Other co-morbidities that could impact the study results such as:
  - o Severe cardiac arrhythmias uncontrolled by medications or pacemaker
  - o Congestive heart failure NYHA III or IV
  - o History of uncontrolled diabetes mellitus

- 
- Significant respiratory disease in which hospitalization may be required
  - Known immunosuppression (i.e. AIDS, post-transplant, undergoing chemotherapy)
20. A known allergy to nickel, titanium, or stainless steel
  21. Unable or unwilling to complete all required questionnaires and follow up assessments
  22. Unable or unwilling to sign informed consent form
  23. Currently enrolled in any other investigational clinical research trial that has not completed the primary endpoint.

**Table 1 : Schedule of Procedures**

Summary of Procedures				
Tests & Assessments	Screening	Procedure through Release	1-3 Day Visit	3 Month Visit (+ 7 days)
Informed Consent	X			
Medical History, including Sexual Function and Catheter Use	X			
Questionnaires				
Urinary Symptoms	X			X
Patient Satisfaction				X
ICIQ-UI Short Form	X			If indicated
Testing Procedures				
UroLift Procedure		X		
Pressure Flow Studies	X			X
UroCuff Test (optional)	X			X
Flexible Cystoscopy with Video	X			
Uroflowmetry	X		X	X
PVR	X		X	X
PSA	X			
UA	X	X	X	X
Urine Culture & Sensitivity	X		If indicated	If indicated
TRUS or Pelvic Ultrasound	X	X		
Review any changes or updates to concomitant medications, adverse events or interventions				
Concomitant Medications	X			X
Adverse Events			X	X
Intervention				X

### 3 STATISTICAL METHODS

Descriptive reports will be provided for this preliminary evaluation. Data will be expressed as the mean  $\pm$  SD for continuous variables and as frequencies for categorical variables.

#### 3.1 Sample Size Justification

As this is a feasibility study, a formal sample size calculation is not required. However, we estimate that the number of participants required to get an initial assessment of urodynamic parameters pre and post PUL with UroLift will be between 10 and 20.

---

### **3.2 Study Objectives**

The aim of this feasibility study is to determine the impact of PUL using the UroLift System on standard pressure flow measures for men with BPH. Feasibility and safety objectives include:

- Feasibility – Assess changes in obstruction and bladder health after PUL with the UroLift System.
- Safety – Determined by the absence of any investigator-reported serious adverse events (SAEs) associated with the device or procedure.

### **3.3 Statistical Methods**

No statistical hypothesis will be tested. Descriptive reports will be provided for this preliminary evaluation. Data will be expressed as the mean  $\pm$  SD for continuous variables and as frequencies for categorical variables.

## **4 ANALYSES**

This is the first exploratory study of the impact of PUL as measured by pressure flow, urodynamic testing (UDS). UDS will be performed at screening and the 3-month follow-up visits and will include an assessment of obstruction and bladder health as measured by Qmax and Pdet@Qmax, and by Pdetmax, and other standard urodynamic parameters. Investigators have the option to use UroCuff, an alternative urodynamic test.

In addition, standard BPH measures such as symptoms, quality of life, uroflowmetry, and post void residual will be evaluated at screening and at the follow-up visits. The analysis of the 3-month data is intended to evaluate the possibility of expanding the scope of the study.

### **4.1 Adverse Events**

Adverse events will be summarized by overall adverse events (AEs), severe AEs (grade 3 or higher on CTCAE scale), AEs related to device and/or procedure, serious adverse events (SAEs), and SAEs related to device and/or procedure separately, and UADEs.

### **4.2 Interim Analysis**

The Urodynamics Feasibility Study will enroll at least 10 patients and then an interim analysis of the urodynamic parameters may be conducted.

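### Should the optional interim look in Section 4.2 be tied to men with paired urodynamic tests rather than to men enrolled?

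*Combined protocol and SAP*

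**What the plan says.** Section 4.2 is one sentence: the study "will enroll at least 10 patients and then an interim analysis of the urodynamic parameters may be conducted". It names no data cut, no minimum number of completed 3-month tests and no use for the result.

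Other sections give the context:

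- Section 3.1 waives a formal calculation ("As this is a feasibility study, a formal sample size calculation is not required") and estimates that the number of men needed for a first reading of urodynamics "pre and post PUL with UroLift will be between 10 and 20".
- Section 4 and Table 1 place pressure-flow testing at screening and at 3 months only. The 3-month visit has a window of plus 7 days.
- Section 4 also states: "The analysis of the 3-month data is intended to evaluate the possibility of expanding the scope of the study". A study goal in the Protocol Summary is "To obtain evidence which may support the design of an expanded study".
- Section 3.3 plans no hypothesis test, only means with SDs and frequencies.
- The Protocol Summary anticipates the first patient in September 2018, the last in February 2019 (at 20 men) and the 3-month analysis in May 2019.

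**The concern.** Two features look wrong at first. First, a man without a 3-month test adds nothing to an estimate of change, so enrolment seems the wrong count. A look taken as soon as the 10th man enters could hold screening data only, or very few pairs. A mean and SD from a handful of pairs would be a poor basis for designing a larger study.

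Second, the look becomes permissible exactly at the lower end of the planned range of 10 to 20, and nothing says how the final number is chosen. If a favourable early result led the sponsor to stop at 10, the reported mean change would tend to be too large, and a reader would not know that the number had been set after seeing data.

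**Working it through.** The plan gives no sample-size formula, SD or effect size, so there is no figure of its own to reproduce. Three checks are possible.

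**1. How many pairs exist when the 10th man enters?**

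Inputs: first patient between 1 and 30 September 2018 and last between 1 and 28 February 2019, so the span S is 124 to 180 days. Assumptions: 20 men evenly spaced, the procedure on the day of enrolment, and 3 months = 91 days.

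- The 10th man enters at day 9S/19: 59 for S = 124 and 85 for S = 180.
- Both are below 91, so even the first man has no 3-month test. Pairs: 0.
- If 18 men instead enter at random between the first and the last, none has reached 91 days with probability P{Binomial(18, 91/S) ≥ 9}: 0.99 for S = 124, 0.86 for S = 152 and 0.61 for S = 180.
- With slower accrual over the same months there are some pairs: 0 to 2 if 15 men are evenly spaced, 3 to 5 if only 10 are.

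So the stated condition can be met with no pairs.

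**2. What is a look on few pairs worth?**

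The 95% half-width for mean change, in SD units, is t(0.975, n−1)/√n. The 95% limits for the SD are the observed SD times √[(n−1)/χ²], using the 97.5% and 2.5% points of χ² on n−1 degrees of freedom.

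| Pairs | Half-width for mean change | Limits for SD (multiple of observed) |
|---|---|---|
| 3 | 4.303/√3 = 2.48 | – |
| 5 | 2.776/√5 = 1.24 | √(4/11.14) = 0.60 to √(4/0.484) = 2.87 |
| 10 | 2.262/√10 = 0.72 | √(9/19.02) = 0.69 to √(9/2.700) = 1.83 |
| 20 | 2.093/√20 = 0.47 | – |

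A look on 3 to 5 pairs would say little. The plan does not propose one, and it plans no confidence intervals; they serve here only as a yardstick.

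**3. Could the look set the final number?**

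- The 10th pair arrives at day 9S/19 + 91: about 150 for S = 124 and 176 for S = 180.
- For S = 124 the last man entered at day 124, so all 20 are in. For S = 180 men enter every 180/19 = 9.47 days, and 176/9.47 = 18.6, so 19 are in.
- In calendar terms the 10th pair falls between 11 February and 11 March 2019, or up to 18 March with the 7-day window. The 3-month analysis is due in May.

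An effect on the final number therefore needs slow or paused accrual, together with a stopping rule that the plan does not contain. To bound its size, assume that enrolment ends at 10 whenever the mean of the first 10 exceeds the true mean, and otherwise runs to 20.

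- Given stopping, the excess is √(2/π)/√10 = 0.252 SD.
- Given continuing, the first 10 are low by 0.252 SD and the mean of 20 by half of that, 0.126 SD.
- Average bias: 0.5 × 0.252 − 0.5 × 0.126 = 0.063 SD, about one-seventh of the 0.47 SD half-width with 20 men.

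**The case for a change.** The best case for a change is that it is cheap and the gap is real. One sentence requiring 10 men with both tests would rule out a look with no usable data, and one clause on enrolment would answer a fair question about the range of 10 to 20. A small feasibility study exists to inform the next one, so an early summary on three or five pairs could mislead.

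Part of this stands: the minimum number of pairs is not written down, and no section says whether the look bears on the final number. The rest is weaker:

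- Section 3.1 ties the same minimum of 10 to pre- and post-procedure urodynamics, so a look at about 10 men with both tests is the natural reading. Section 4.2 gives the earliest point for an optional look and does not require it at once.
- The documents attach the expansion decision to the 3-month analysis, not to the interim look.
- A fixed minimum of 10 pairs brings little. If the final number is 10, the look is the final analysis, and one dropout or unusable tracing means it never happens. If 20 men enter on schedule, it comes when enrolment is essentially complete.

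**Conclusion.** No change to the plan is needed. Section 4.2 lacks detail, but following it as written leaves the final descriptive results sound. The look is optional and carries no decision, there is no type I error to protect, and the text allows the analyst to wait for paired data. Anyone summarising interim change would have to count the men with both tests and would report that count, which shows the reader how little a small number can support. If the look did influence where enrolment ended, the report should say so; that is ordinary reporting practice.

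The finding of no pairs at the 10th enrolment rests on even accrual of 20 men over the anticipated months and treatment on the day of enrolment; slower accrual would give a few pairs. The bias of about 0.06 SD rests on an invented stopping rule and normally distributed changes. It bounds a hypothetical and is not a finding about this trial. Among studies that did stop early under that rule the excess would be larger, 0.25 SD, but on the planned timeline the situation hardly arises.
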